### 6.1 Overview of the study design and dose regimen

This is a Phase III, multi-center, randomized, 48 weeks, double-blind, parallel-group, placebo-controlled study to evaluate efficacy and safety of CER-001 on ApoA-1 and vessel wall area in patients with genetically defined familial primary hypoalphalipoproteinemia and receiving background optimized lipid therapy.

Double-blind treatment phase: After obtaining written informed consent and provided the patient fulfills the selection criteria as defined in *section 7*, he/she will be randomized to receive twenty-nine doses of CER-001 or placebo, weekly during the first 8 weeks (9 doses) and then every two weeks during the following 40 weeks (20 doses). Dosing visits will have a window of +/- 2 days around the strict weekly or biweekly date.

Open-labeled treatment phase: After obtaining written informed consent, patient will receive twelve doses of CER-001, one every two weeks during 24 weeks following the last dose administered during double-blind treatment period. Dosing visits will have a window of +/- 2 days around the strict biweekly date.

Patients will have a safety follow-up visit at least 30 days after the last dose administered.

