## **9.6 Method of Administration**

CER-001 is provided as a frozen solution in 20 mL vials containing at least 17.2 mL of product at a concentration of 8 mg/mL (ApoA-1 content).

CER-001 will be constituted into an IV dosing solution by the Study Pharmacist or designee by diluting with normal saline. All doses will be diluted with normal saline to a volume of 250 mL and will be administered over a one-hour period using an infusion pump at a fixed rate of 250 mL/hr. Study drug administration may be extended up to a period of 120 minutes if deemed medically necessary for the patient by the Investigator (e.g. concern for fluid overload). Reasons for administration periods greater than 60 minutes must be properly documented. Patients should be observed for a minimum of 15 minutes following the infusion.

Placebo, standard 250 mL sodium chloride solution, is provided and will be administered over a one-hour period using an infusion pump at a fixed rate of 250 mL/hr.

Patients should be observed for a minimum of 15 minutes following the infusion.

The Study Pharmacist or designee will dispense the appropriate concentration and volume of solution for each patient, based on his/her weight at Screening. The infusion bag and drip set will be sent from the pharmacy with the infusion bag shrouded with a bag to maintain the blind.

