7.3.2 Treatment compliance

Treatment compliance will be assessed on the mITT population according to randomized treatment group. Compliance (%) with the study treatment will be summarized on each study period (Induction / Maintenance / Extension) and at W24, W48 as follows:

- Compliance during induction phase (%) = Number of infusions totally administered between W0 and W8 / 9 * 100
- Compliance during maintenance phase (%) = Number of infusions totally administered between W10 and W24 / 8* 100
- Compliance during extension phase(%) = Number of infusions totally administered between W26 and W48 / 12 * 100
- Compliance at W24 (%) = Number of infusions totally administered between W0 and W24 / 17
 * 100
- Compliance at W48 (%) = Number of infusions totally administered between W0 and W48 / 29* 100

Average dose, total dose of CER-001 as well as administered dose *vs* expected dose will be summarized at W8, W24, W48, and are defined as follows:

- Total dose at Wi (mg) = $\sum_{v=1}^{ni} CER001$ dose prescription for infusion $v\left(\frac{mg}{kg}\right)$ * Weight at infusion $v\left(kg\right)$ * Actual volume administered at infusion $v\left(mL\right)$ / 250, when n_i = number of infusions received between W0 and Wi
- Average dose at Wi (mg) = Total dose at Wi (mg) / number of infusions received between WO and Wi
- Administered dose vs expected dose at Wi (%) = Total dose at Wi (mg) / (8 * $\sum_{v=1}^{mi} Weight$ at infusion v) * 100, when m_i = number of infusions planned between W0 and Wi

In addition, a by-patient listing will be produced for each patient who verified for at least one visit:

- Dose prescription different from 8 mg/kg
- Time elapsed between study medication infusion preparation and study medication administration > 72h (48h for Canadian sites)
- Start infusion time stop infusion time > 65 min or < 55 min
- Total volume administered = No

For these patients, the listing will include, for all available visits:

- Patient ID, visit, treatment arm
- Dose prescription (mg/kg)
- Date and time of study medication infusion preparation
- Date of infusion, start and stop infusion time
- If not administered, reason
- If infusion duration different from 60 min, reason

CER-001-CLIN-009 CER-001

- Total volume administered (Yes/No)
- If No, volume administered (mL)

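### SAP 7.3.2 computes CER-001 mg from weight at each infusion, but Protocol 9.6 prepares bags from screening weight, and no rule covers the 21 of 29 infusions without a scheduled weight

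*SAP*

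**What the plan says.** **Preparation.** Protocol 9.6 has the pharmacist "dispense the appropriate concentration and volume of solution for each patient, based on his/her weight at Screening". It adds: "All doses will be diluted with normal saline to a volume of 250 mL". Neither document contains a rule that updates this weight later in the trial.

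**Reported dose.** SAP 7.3.2 defines three mg-based quantities at W8, W24 and W48. The weight term in its formulas is "Weight at infusion":

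- Total dose: the sum, over the "number of infusions received between W0 and Wi", of prescribed mg/kg × weight at that infusion × volume administered / 250.
- Average dose: total dose divided by the number of infusions received.
- Administered versus expected dose: total dose divided by 8 × the sum of weight at infusion, the sum running over the "number of infusions planned between W0 and Wi".

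**When weight is taken.** Weight belongs to the V2 assessments (Protocol 8.2) and to the complete assessments at W4, W8, W16, W24, W32, W40 and W48 (Protocol 8.3, Appendix A). SAP 7.5.2 uses the same time points, plus screening and follow-up.

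**Missing weights.** SAP 7.1.4 and 7.5.2 replace a missing W0 value by the screening value. They do not address weight at later infusions. SAP section 10 declares a change of efficacy model and nothing about dosing weight.

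**The concern.** An exposure summary should report the mg that were in the bag multiplied by the fraction infused. By Protocol 9.6 the content of the bag depends on screening weight. The SAP formula uses another weight, so for a patient whose weight has changed it returns a figure that is neither dispensed nor infused. Screening can last up to 16 weeks (Protocol 6.1.1), so the two weights can already differ at the first dose.

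Most of the weights that the formula asks for are also not scheduled. A programmer would have to invent a rule, and different rules give different totals.

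At stake are total and average mg and, for patients with missed, reduced or incomplete infusions, the administered-versus-expected percentage. SAP 7.5.1 also asks for an absolute amount of study drug in the individual listings of deaths, other SAEs and other significant AEs. It defines no separate calculation, so the same ambiguity could carry over there.

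**Working it through.** **1. The plan's own infusion counts.** Weekly from W0 to W8 gives 9 infusions. Every two weeks from W10 to W48 gives 20, of which 8 fall in W10–W24 and 12 in W26–W48. So 9 + 8 = 17 to W24 and 9 + 20 = 29 to W48. These match the SAP denominators, including "Number of infusions totally administered between W0 and W48 / 29* 100".

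**2. Infusions with a scheduled weight.**

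| Up to | Infusions | With scheduled weight | Without |
|---|---|---|---|
| W8 | 9 | 3 (W0, W4, W8) | 6 |
| W24 | 17 | 5 (adds W16, W24) | 12 |
| W48 | 29 | 8 (adds W32, W40, W48) | 21 (21/29 = 72%) |

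**3. Error per infusion.** Let d be the prescribed mg/kg and V the volume infused.

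- mg given = d × screening weight × V/250
- mg reported = d × weight at infusion × V/250
- reported / given = weight at infusion / screening weight

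**4. Size at W48.** The documents give no data on weight change, so the changes below are assumptions, as is a screening weight of 80 kg. All bags are taken as complete at 8 mg/kg, so the dose given is 8 × 80 × 29 = 18,560 mg. The last measured weight is carried forward, which is a rule the SAP does not state.

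| Assumed weight change | Reported mg | Error |
|---|---|---|
| None | 18,560 | 0 |
| ±2% from the first infusion | 18,189 / 18,931 | ±2% |
| ±5% from the first infusion | 17,632 / 19,488 | ±5% |
| ±10% from the first infusion | 16,704 / 20,416 | ±10% |
| ±5%, linear over 48 weeks | 18,197 / 18,923 | ±1.95% |
| ±10%, linear over 48 weeks | 17,835 / 19,285 | ±3.91% |

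Hand check of the linear 5% case: the infusion weeks sum to 616, with mean 616/29 = 21.2. With weight known at every infusion the error is 5% × 21.2/48 = 2.2%. Carrying weights forward gives a mean week of 544/29 = 18.8 and 5% × 18.8/48 = 1.95%.

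**5. Dependence on the unstated rule.** If a program simply dropped infusions without a weight, the W48 total at stable weight would be 8/29 = 28% of the dose given. This shows why a rule is needed. It does not predict what the CRO would do.

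**6. The ratio.** With all bags complete at 8 mg/kg, numerator and denominator are the same sum, so the ratio is 100% whatever weights are used. With one fixed weight per patient, the weight cancels for every patient: the ratio becomes the sum of d × V/250 over received infusions, divided by 8 × the number planned. With a weight that varies by infusion it does not cancel once infusions are missed, and the denominator then needs weights for infusions that did not take place.

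**The case against.** The strongest reply is that the CRF is not among the documents. The SAP was written from it, and 7.3.2 uses infusion-level fields such as preparation time, prescribed mg/kg and volume. If the weight field for each infusion holds the weight used for preparation, the formula is correct and needs no 29 measured weights. That possibility stands. But the SAP does not say so, and read as written its term conflicts with Protocol 9.6.

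A reader might infer that the weights at missed infusions cannot exist, so that the ratio cannot be computed. The documents do not support this. Protocol 8.7 provides for full assessments every 8 weeks after early stopping (before W24, if the patient agrees to stay in the study), and these include weight. Some missed infusions will therefore have one. What is lacking is a rule for the rest.

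It is also fair that these are descriptive summaries. The five compliance percentages count infusions, no efficacy model in SAP 7.4 uses mg, and prescriptions other than 8 mg/kg and incomplete volumes are listed by patient anyway. This limits the importance of the point but does not remove it.

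**Conclusion.** The point holds as a minor error in exposure reporting. As the SAP is written, total and average mg are wrong in proportion to any departure from screening weight: not at all at stable weight, about 2% at W48 for a linear 5% drift, and 2% to 10% if a change of that size is present from the first infusion. The sizes rest on assumed weight changes. The conclusion assumes that bags are prepared as Protocol 9.6 reads and that the SAP term means weight at that visit.

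Two stronger readings are tempting and should be resisted. One is that the reported total is never the dose given; the two agree whenever weight is unchanged, or if the CRF field holds the preparation weight. The other is that 72% of the reported mg is in error; 72% is the share of infusions without a scheduled weight. The primary endpoint and the sample size are not touched.

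**What to change.** First reconcile Protocol 9.6 with SAP 7.3.2, and check what the CRF records as weight for each infusion. Then define the weight term, in the two formulas that contain it (total dose and the expected-dose denominator), as the weight on which the bag was actually prepared. As 9.6 reads, that is screening weight. Apply it to received and planned infusions alike; average dose inherits the change. If a per-visit weight is kept anywhere, state the rule for infusions at which none was taken.

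This takes no position on which weight should govern dosing. It only makes the reported mg equal the mg dispensed and infused.

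The cost is a line or two of SAP text before database lock. Screening weight is already collected, so no new data are needed.

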7.4 Efficacy data

7.4.1 Primary endpoint

The primary efficacy endpoint is defined as the difference in the change from baseline in carotid artery MVWA at 24 weeks in patients treated with CER-001 compared to patients treated with placebo.

Analysis of the primary endpoint will consist of a main analysis, a supportive analysis and several sensitivity analyses.

7.4.1.1 Main analysis

A linear mixed model with repeated measures (MMRM) will be fitted to observed data for the mITT population without any imputation. An unstructured covariance matrix will be used to model random effects. The model will include the following variables:

- Change from baseline in carotid artery MVWA (mm², dependent variable)
- Randomized treatment group (CER-001 vs Placebo, independent variable)
- Genetic mutation (ABCA-1/ApoA-1/ABCA-1 and ApoA-1), independent variable)
- Carotid artery MVWA at W0 (mm², covariate)
- Visit (W8/W24/W48, independent variable)
- Treatment-by-Visit interaction (independent variable)
- Carotid artery MVWA at W0 by Visit interaction (independent variable)
- Treatment-by-carotid artery MVWA at W0 (independent variable)
- Subject (random factor)

Sample SAS Code

```
proc mixed data=DATASET method=reml covtest asycov alpha=0.05;

class USUBJID TRTGRP (ref="Placebo") VISIT (ref=LAST) GENETIC_MUT (ref="REF");

model CHANGE = BASELINE GENETIC_MUT BASELINE*VISIT TRTGRP VISIT

VISIT*TRTGRP BASELINE*TRTGRP / s ddfm=kr;

repeated visit / subject=USUBJID type=UN r rcorr;

lsmeans VISIT*TRTGRP / diff cl om e;

estimate "Treatment Effect" TRTGRP 1 -1 VISIT*TRTGRP 0 1 0 0 -1 0 / cl;

run;
```

Adjusted means in change from baseline for each treatment group (with 95%CI) as well as treatment effect (with 95%CI) at W24 will be provided. Treatment effect will be calculated as the difference in adjusted mean values for the two treatment groups at W24.

Adjusted means in change from baseline and treatment effect will also be estimated at W24 within each genetic mutation subgroup.

CER-001-CLIN-009 CER-001

A scatter plot will also be drawn representing the evolution of the carotid artery MVWA (mm²) according to the carotid artery MVWA at week 0 (mm²) grouped by treatment group.

Adjusted means (with 95%CI) of each randomized treatment group will also be plotted.

Results will be displayed according to table 5 of section 12.1.

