### **12.2 Efficacy Assessments**

#### **12.2.1 Primary Efficacy Analysis**

The primary efficacy parameter of this study will be the change from baseline to 24 weeks in carotid MVWA in all randomised patients.

The primary efficacy endpoint, difference in the change from baseline in carotid artery Mean Vessel Wall Area (MVWA) at 24 weeks in patients treated with CER-001 compared to patients treated with placebo, will be analysed by an analysis of covariance (ANCOVA) model that includes treatment group and baseline MVWA as well as ABCA-1 or ApoA-1 genetic mutation as a covariate. Adjusted means for the change in MVWA in each treatment group and the difference between CER-01 and placebo will be provided, along with a 95% confidence interval.

Results (in terms of 95% confidence intervals for treatment effects) will also be presented for each of the ABCA-1 and ApoA-1 subgroups.

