1.3 Exploratory objectives

[figure not shown]
The exploratory objectives of the study are:

- To evaluate the effect of treatment with CER-001 with respect to other efficacy measurements including carotid artery and carotid normalized wall index using 3T-MRI;
- To evaluate the effect of treatment with CER-001 with respect to potential surrogate markers on vessel wall biology including laboratory variables;
- To evaluate the effect of treatment with CER-001 with respect to inflammation;
- To evaluate plasma-mediated cellular Cholesterol efflux capacity;
- To measure ApoA-1 levels (pharmacokinetic parameters);
- To measure Cholesterols, triglycerides, lipids, apolipoprotein and lipoprotein levels (pharmacodynamics parameters).

2. Study summary

This is a phase III, multi-centre, randomized, 48 weeks, double-blind, parallel-group, placebo-controlled study to evaluate efficacy and safety of CER-001 on ApoA-1 and vessel wall area in patients with genetically defined familial primary hypoalphalipoproteinemia and receiving background optimized lipid therapy.

The study design is illustrated in the following figure:

3. Sample size

The assumptions upon which the power calculations are based are data from the 7 patients completing the CER-001-CLIN-007 SAMBA study, given the similarity of the genetic mutations. Those patients presented with a median value for MVWA of 25.0 mm² and had a follow-up median value at 6 months of 21.8 mm². The mean percent reduction is reported as 6.7%, standard deviation = 4.5%. These observed values would provide a conservative estimate of the effect of CER-001 in the more severe population for this FPHA study.

Using these results from SAMBA (i.e. an assumed standard deviation of 4.5%) and a 2:1 randomization scheme to maximize exposure to active drug, 16 completing patients in the CER-001 group and 8 in the placebo group (24 total completers for mITT) would yield 90% power to detect a difference from baseline versus placebo of 6.7%, using two-tailed testing with α =0.05. A total of 30 patients are planned to be randomized that would provide a buffer such that a 20% discontinuation rate would still allow the study to retain sufficient power for a supporting per protocol efficacy analysis (MVWA).

CER-001-CLIN-009 CER-001

4. Randomization

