7.4.2.2 Change from baseline in femoral artery MVWA

A linear mixed model with repeated measures (MMRM) will be fitted to observed data for the mITT population without any imputation. An unstructured covariance matrix will be used to model random effects. The model will include the following variables:

- Change from baseline in femoral artery MVWA (mm², dependent variable)
- Randomized treatment group (CER-001 vs Placebo, independent variable)
- Genetic mutation (ABCA-1/ApoA-1/ABCA-1 and ApoA-1), independent variable)
- Femoral artery MVWA at W0 (mm², covariate)
- Visit (W8/W24/W48, independent variable)
- Treatment-by-Visit interaction (independent variable)
- Femoral artery MVWA at W0 by Visit interaction (independent variable)
- Treatment-by-femoral artery MVWA at W0 (independent variable)
- Subject (random factor)

Analysis will be based on that described for the main analysis of the primary endpoint (section 7.4.1.1). No multiple imputation will be performed.

The following differences between placebo and the experimental treatment will be estimated:

- Change from baseline (W0) in femoral artery MVWA at 8 weeks
- Change from baseline (W0) in femoral artery MVWA at 24 weeks
- Change from baseline (W0) in femoral artery MVWA at 48 weeks.

These estimators will also be calculated within each genetic mutation.

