7.4.2.3 Change from baseline in target (plaque) to background (blood) ratio

An analysis of covariance (ANCOVA) will be fitted to observed data for the mITT population without any imputation. The model will include the following variables:

- Change from baseline (W0) in TBR based on standardized 18FDG uptake measured with 18FDG-PET/CT MVWA at 24 weeks (dependent variable)
- Randomized treatment group (CER-001 vs Placebo, independent variable)
- Genetic mutation (ABCA-1/ApoA-1/ABCA-1 and ApoA-1), independent variable)
- TBR at W0 (covariate)
- Interaction Treatment by TBR at W0 (independent variable)

Adjusted means for the change in TBR and the associated 95%CI will be provided for each randomized treatment group. Adjusted mean difference and the associated 95%CI will also be displayed.

CER-001-CLIN-009 CER-001

Sample SAS Code

```
proc glm data=DATWIDE alpha=0.05;
    class TRTGRP GENETIC_MUT;
    model CHANGE24 = BASELINE GENETIC_MUT BASELINE*TRTGRP TRTGRP / s;
    lsmeans TRTGRP / cl pdiff=control("REF");
run;
```

The previous statistics will also be estimated within each genetic mutation.

A scatter plot will be drawn representing the evolution of the TBR at week 24 according to the baseline TBR grouped by treatment group. Adjusted means (with 95%CI) for the change from baseline in each randomized treatment group will also be plotted.

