7.7 Listings of individual data

All collected data and derived variables used for the statistical analysis will also be presented in individual patient listings, in accordance with ICH appendix 16.2. Each patient will be identified in these listings by his/her unique patient number.

8. Interim analyses

No interim analysis is planned.

9. Data and Safety Monitoring Board

The Data and Safety Monitoring Board (DSMB) will formally review unblinded study safety data to ensure there is no avoidable increased risk for harm to patients. Analyses for the DSMB meetings will be performed by an independent statistician (different from the one who will perform the final analysis). A specific SAP displays the safety data generated needed for the DSMB review.

10. Modifications with respect to the protocol

Analysis of efficacy endpoints

Statistical analysis of the primary and secondary outcomes (changes from baseline) were modified with respect to the protocol. In order to gain in terms of power, model will be fitted using all observations available for each patient during the study. Hence, linear mixed model with repeated measures will be used instead of analysis of covariance, Changes from baseline for a specified outcome could therefore be estimated at different time points based on the same model.

CER-001-CLIN-009 CER-001

11. Approval of the Statistical Analysis Plan

ICTA PM	SPONSOR
Project Manager:	Sr VP Clinical Development & Operations:
[name]	[name]
Date:	Date:
Signature:	Signature:
Biostatistician:	
[name]	
Date:	
Signature:	
Head of Medical and Scientific Development:	
[name]	
Date:	
Signature:	

CER-001-CLIN-009

12. Appendices

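### The SAP adds an undeclared treatment-by-baseline interaction to the carotid, femoral and TBR models; the precision cost is small, but as coded it moves the carotid treatment contrast to a baseline of 0 mm².

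*SAP*

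**What the plan says.** Protocol 12.2.1 specifies an ANCOVA that "includes treatment group and baseline MVWA as well as ABCA-1 or ApoA-1 genetic mutation as a covariate". Protocol 12.2.2 uses a similar model for the secondary endpoints. Neither has a treatment-by-baseline term.

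The SAP has one in three places:
- 7.4.1.1 (carotid, primary): "Treatment-by-carotid artery MVWA at W0 (independent variable"
- 7.4.2.2 (femoral): "Treatment-by-femoral artery MVWA at W0 (independent variable"
- 7.4.2.3 (TBR): "Interaction Treatment by TBR at W0 (independent variable"

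The sample code in 7.4.1.1 and 7.4.2.3 carries it as `BASELINE*TRTGRP`.

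The SAP introduction says that changes to the protocol will be reported in section 10. Section 10 declares only the move from ANCOVA to a repeated-measures mixed model, for this reason: "In order to gain in terms of power, model will be fitted using all observations available for each patient during the study". TBR stays an ANCOVA, so that declaration does not cover its extra term. No rationale for the interaction is given.

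SAP 7.4.1.1 defines the treatment effect as the difference between the two adjusted means at W24. The code beneath it has an `LSMEANS` line and an `ESTIMATE` line. The `ESTIMATE` line lists coefficients for treatment and visit-by-treatment only. In the SAP 12.1 templates, Table 6 has a treatment row and an interaction row. Table 8 (TBR) has a treatment row but no interaction row. Table 7 reports differences in LS-means.

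**The concern.** Once treatment interacts with baseline, the treatment coefficient by itself is the effect for a patient whose baseline is zero. The effect at a realistic baseline is that coefficient plus the interaction slope times the baseline value. Two things follow.

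First, the model needs a separate baseline slope in the placebo arm, where about 8 completers are planned. PET/CT is done only at equipped sites, so TBR may have fewer. This costs some precision, while section 10 gives power as the reason for changing the model.

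Second, any output that reports the treatment coefficient without the interaction answers a question about a vessel with no wall area. At stake is whether the line labelled as the treatment effect in the primary analysis code estimates what the text of the same section defines.

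**Working it through.** **1. The plan's own figure.** Inputs from SAP section 3: "The mean percent reduction is reported as 6.7%, standard deviation = 4.5" (percent); 16 and 8 completers; "two-tailed testing with α =0.05". The claim is that this "would yield 90% power to detect a difference from baseline versus placebo of 6.7" (percent).

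SE = 4.5 × √(1/16 + 1/8) = 4.5 × 0.4330 = 1.949. Noncentrality = 6.7/1.949 = 3.44. A two-sample t-test with 22 df has power 90.7%, so the stated 90% is reproduced. Also 24/0.8 = 30, the planned number randomised.

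**2. Cost when the effect is read at the mean baseline.** With separate slopes and no mutation term, the variance of the effect at baseline x is

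σ² × [1/16 + 1/8 + (x − mean_T)²/S_T + (x − mean_P)²/S_P],

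where T is CER-001, P is placebo, and S is the within-arm sum of squares of baseline. At the overall mean, the last two terms arise only from baseline imbalance between arms. Simulated designs (normal baseline, two mutation levels, equal true slopes) give:

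| Setting | Without term | With term | Change |
|---|---|---|---|
| 16:8, 4.5 as residual SD | power 87.5% | 85.8% | variance about +5%, SE about +2.2% |
| 16:8, baseline-change correlation −0.3 | power 90.3% | 88.8% | variance +5%, CI 2.4% wider |
| 20:10, 4.5 as residual SD | power 94.4% | 93.7% | SE about +1.5% |
| Three-visit repeated measures, 16:8, complete data, no mutation term | – | – | SE +1.1% to +1.7% |

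At 16:8 without the mutation factor, the median SE increase is 0.5% and the 95th percentile 8.5%. The cost is usually negligible and occasionally visible when the arms differ at baseline.

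For TBR the documents give no number of PET/CT patients. With 10:5 (assumed) the variance rises about 14% and the CI widens 7%; with 8:4 (assumed), about 30% and 12%.

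**3. The coded contrast.** The `ESTIMATE` line has no `BASELINE*TRTGRP` coefficient. If the software takes it as zero and baseline is uncentred, x = 0 in the formula. Let k be baseline mean/SD. The documents give a median MVWA of 25.0 mm² in the earlier single-arm study but no SD, so k is assumed. With balanced arms, S_T ≈ 15 SD² and S_P ≈ 7 SD², and the bracket becomes 0.1875 + k²/15 + k²/7:

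- k = 3: 0.1875 + 0.600 + 1.286 = 2.073; SE ratio √(2.073/0.1875) = 3.3
- k = 5: 0.1875 + 1.667 + 3.571 = 5.426; SE ratio 5.4
- k = 8: 0.1875 + 4.267 + 9.143 = 13.597; SE ratio 8.5

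Simulation, which lets the sums of squares vary and includes mutation, gives SE ratios of 3.6, 5.9 and 9.3. Power falls to about 15%, 9% and 6.5%. In the repeated-measures model at k = 5 the SE ratio is 4.3 to 5.4.

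These powers assume the same true effect at every baseline. The plan is powered in percent change. If the effect is a constant percentage of baseline, the true effect in mm² at a baseline of 0 is zero, and the coded contrast has nothing to detect.

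**4. Tables.** The Table 6 treatment row, used for carotid and femoral, is the same kind of coefficient: with W48 as the reference visit, it is the W48 effect at a baseline of 0 mm². The Table 8 CER-001 row is the effect at TBR = 0, and without an interaction row the reader cannot convert it.

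**The case against.** The term is prespecified. It is in the SAP text, the code and Table 6. The SAP says that it supersedes the protocol and that decisions precede unblinding, and protocol 12.1 refers to the SAP for detail. This stands: the defect is non-declaration, not concealment.

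A reader might infer that the treatment effect now rests on a slope from about 8 placebo patients, or that it no longer has a single value. The documents do not support either. SAP 7.4.1.1 fixes one W24 difference in adjusted means and Table 7 reports one LS-means difference per visit. Read there, the placebo slope matters mainly when the arms are imbalanced at baseline. With so few placebo patients the estimate is somewhat more sensitive to such imbalance, and no more than that.

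Nor can one infer that the headline result will be wrong. The code is labelled as sample code, and Table 7 points to the `LSMEANS` output. But the SAP does not say which output supplies the reported or pooled estimate, and the two lines disagree.

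The simulations in step 2 assume equal true slopes, where the term can only cost. If slopes differ, deleting it can lose power. With assumed baseline mean 25 and SD 7 mm² and a slope difference of 0.15 mm² per mm² (assumed), power drops from 84.9% to 81.5%. Under a constant percent effect, deletion still gains about 2 points (82.9% to 84.8%). So the precision argument for deletion is weak in either direction; the consistency argument is not.

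**Conclusion.** The interaction is in all three SAP models, absent from the protocol's model, and undeclared in section 10. Under the adjusted-means definition its cost is small: about +5% variance and 1 to 2 power points at 16:8 in a single-visit ANCOVA, and 1% to 2% on the SE with repeated measures. The TBR cost could be larger, but its size rests on assumed PET/CT numbers.

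The more serious consequence is in the code. The `ESTIMATE` line contradicts the definition in its own section and, taken literally, targets a baseline of 0 mm² with power of roughly 6% to 15%. That range assumes that unlisted coefficients are zero, that baseline is uncentred, and that baseline mean/SD is 3 to 8. The treatment rows of Tables 6 and 8 are affected in the same way. This should be corrected before unblinding. It does not show that the planned Table 7 comparison is invalid.

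**What to change.** Delete the treatment-by-baseline term from 7.4.1.1, 7.4.2.2 and 7.4.2.3, from the sample code, and from Table 6. Fit it once as an exploratory check of effect modification at W24. The covariates then match protocol 12.2.1 apart from the declared repeated-measures structure. The existing `ESTIMATE` line equals the W24 adjusted-mean difference, provided both arms are read at the same baseline and mutation mix, and the treatment rows of Tables 6 and 8 no longer refer to a zero baseline.

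If the sponsor keeps the term:
- declare and justify it in section 10, including for TBR;
- centre baseline, or add the `BASELINE*TRTGRP` coefficients at the mean baseline to the `ESTIMATE` line;
- correct the treatment rows of Tables 6 and 8 and add an interaction row to Table 8.

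The cost is SAP wording, code and table templates. The downside of deletion is that a true slope difference between arms would show only in the exploratory model, and the primary model could then lose a little power.
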